10.4 Multiple Comparisons and Multiplicity

Type I error rate adjustment is not applicable as there is no confirmatory test planned in this study. The efficacy analysis is exploratory, and no statistical tests are planned.

10.5 Missing Data and Imputation

Missing efficacy data will not be imputed, as there is no formal statistical analysis planned. All subjects who drop out without completing the first 30 days of the treatment period will be regarded as missing for all efficacy analysis.

There will be no imputation of partial or complete missing dates.

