3.4 Planned Study Duration

The duration of the study for a **CSL312-naïve subject** is expected to be a minimum of 17 months. This estimation is based on:

- An up to 1-month Screening Period.
- An up to 2-month Run-in Period.
- A minimum of a 12-month Treatment Period.
- A 2-month Follow-up Period.

The duration of the study for a **previously treated CSL312 subject** is expected to be a minimum of 14 months in this study. This estimation is based on:

- A minimum of a 12-month Treatment Period.
- A 2-month Follow-up Period.

Per Amendment 1, the duration of treatment for an individual subject is estimated to be a minimum of 12 months. The treatment duration for each subject will be variable. In addition, the study may be stopped in a specific country either after garadacimab obtains regulatory approval or it becomes commercially available in the respective country. The Sponsor reserves the right to stop the study at any time.

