10.2.1 Secondary Efficacy Analysis

The secondary efficacy endpoints will be analyzed using the ATS Analysis Set. The endpoint “Time-normalized number of HAE attacks” will also be analyzed using the PP Analysis Set. All efficacy analysis will not differentiate between treatment administration with NSD or AI and will be based on the overall Treatment/Efficacy evaluation period.

Subjects will enter HAE symptoms into their eDiary and the start and end date and time, the interference of HAE symptom(s) with daily activities, and location(s) of the HAE symptom(s). Investigator-reported HAE attacks will be based upon review of subject diaries, relevant interval medical history, and physician judgment. The investigator may ask clarifying questions to assist in his / her assessment of whether an HAE attack occurred. If an attack occurred, the investigator will record an attack in the eCRF, the start/end date, the attack location(s), and the severity of the attack based on the most severe symptoms.

For all analyses considering HAE attacks, only the HAE attacks confirmed and reported by the investigator using the eCRF ‘HAE Attacks’ form will be used.

For CSL312-naïve subjects, HAE attacks with a start date on or after the first day of the Run-in Period but prior to the date and time of the first study drug administration will be counted for the Run-in Period. For subjects from CSL312_2001 and CSL312_3001 the number of HAE attacks in the Run-in Period of the previous study will be used. The HAE attacks that occurred during the Run-in Period of the lead-in study will be imported from the final analysis datasets of the respective lead-in study.

HAE attacks with a start date and time after the first study drug administration through the EOT Visit will be counted for the Treatment Period and will be included in the analyses of efficacy.

HAE attacks will be listed, including start date/time, end date/time, time between start of the attack and end of the most recent preceding attack, anatomical locations, severity, most recent actual CSL312 dose (loading dose of 400 mg or the monthly 200 mg dose), injection device (NSD or AI), potential trigger, duration in days, period in which the HAE attack occurred and how many on-demand medications were taken per HAE attack.

The following derived endpoints based on HAE attacks will be presented together in a listing:

- Time-normalized number of HAE attacks (per month and per year),

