- Time-normalized number of HAE attacks requiring on-demand treatment (per month and per year),
- Time-normalized number of HAE attacks with moderate or severe severity (per month and per year),
- Duration of the treatment period,
- Total number of HAE attacks,
- Reduction in Attack Rate (Treatment period versus Run-in),
- Time to first attack (in days),
- Maximum Time between attacks.

Subjects excluded from the efficacy analysis will be presented in a listing, including the reason for exclusion.

Possible reasons for exclusion from efficacy analysis include exclusion from the ATS Analysis Set and insufficient time spent in the study which is defined as a Treatment/Efficacy evaluation period duration of less than 30 days.

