10.2.1.1 Time-normalized number of HAE attacks

The time-normalized number (per month) of HAE attacks is calculated per subject as:

$$\frac{\text{the number of HAE attacks}}{\text{length of subject treatment in days}} * 30.4375$$

where the length of subject treatment is calculated as the duration of the Treatment/Efficacy evaluation period described in [Section 8.4](#).

To transform the length of subject treatment which is calculated in days in years the number of days is divided by 365.25. Thus, time-normalized number of HAE attacks per year is calculated per subject as:

$$\frac{\text{the number of HAE attacks}}{\text{length of subject treatment in days}} * 365.25$$

The time-normalized number of HAE attacks will also be calculated for the Run-in Period. For non-CSL312-naïve subjects, the Run-in Period of their previous CSL312 study will be used.

The time-normalized number of HAE attacks per month and per year will be summarized descriptively including median (primary measure of interest) and mean (secondary measure of interest) with corresponding 95% CIs. The CIs for the mean will be based on the t-distribution while distribution-free CIs will be used for the median.

Besides the time-normalized number of HAE attacks, the total number of HAE attacks (ie, not time-normalized) will also be summarized.

10.2.1.2 The Reduction in the Attack Rate during the Treatment Period compared to the Run-in Period

The secondary efficacy endpoint of the percentage reduction in the time-normalized number of HAE attacks is calculated within a subject as:

$$100 * \left(1 - \frac{\text{time normalized number of HAE attacks per month during treatment}}{\text{time-normalized number of HAE attacks per month during Run-in}} \right)$$

and will be summarized descriptively. For non-CSL312-naïve subjects, the Run-in Period of their previous CSL312 study will be used.

The number and percentage of responders and non-responders will be presented combined with corresponding 95% CI. A subject is classified as a responder if the percentage reduction in HAE attacks under treatment compared to the Run-in Period is $\geq 50\%$. In addition, the number and percentage of subjects with percentage reductions of $\geq 70\%$ and $\geq 90\%$ will be presented with corresponding 95% CIs.

Furthermore, the number and percentage of subjects with a percentage reduction of 100%, ie, who are attack-free, will be presented and summarized with corresponding 95% CI.

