10.3.1 Time to Event Analysis

The following events will be analyzed only for treatment-naïve subjects:

- Time from Visit Day 1 to start of first HAE attack.
- Time to first HAE attack after Day 14.
- Time from end of first HAE attack to start of second HAE attack. (only for subjects experiencing at least one attack).
- Time from end of second to start of third HAE attack (only for subjects experiencing a second attack).

The following will be analyzed for all subjects in the ATS Analysis Set instead of only for treatment-naïve subjects:

- Maximum attack-free time.

The time to event will be derived as described in [Section 8.2.2](#) within the Treatment/Efficacy evaluation period.

Attack-free time between subsequent HAE attacks is calculated as start date/time of the following HAE attack – end date/time of the preceding HAE attack. Subjects with no HAE attack or no second or third HAE attack will be censored at EOT Visit.

For each of the HAE events (1st, 2nd, 3rd attack and 1st attack after Day 14) the following will be displayed:

- The number and percentage of subjects who do not experience the event.
- The median time, the 25% and 75% percentile times of subjects being event-free / having no second / having no third HAE attack, respectively. The median, 25%, and 75% percentile times are defined as the times for which the Kaplan-Meier estimates for the time-to-event functions are equal 0.5, 0.25, and 0.75, respectively.

If the time to event function is horizontal at 25%, 50% or 75%, the median or percentiles will be calculated as the average of the two values between which the time-to-event function is horizontal.

- The minimum and maximum times to the event.

Kaplan-Meier curves with 95% CI will be plotted showing the percentage of subjects being event-free at certain times.

The corresponding life tables will also be presented.

The maximum attack-free time will be summarized by the median time, the 25% and 75% percentile times and the minimum and maximum times to the event.

The number and percentage of subjects who have a maximum attack-free time of at least 6 months and of at least 12 months will also be displayed in the summary for maximum attack-free time.

By-subject listings will be provided with time until the first, the second and the third HAE attack as applicable, or until EOT Visit with indication whether the observation is censored. The maximum attack-free time will be flagged.

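### The whole-period attack-free percentage has no fixed time horizon, so it falls as follow-up lengthens, and the 30-day rule drops observed early attacks from the time-to-event analysis

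*SAP*

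**What the plan says.** **Attack-free percentage.** SAP 10.2.1.2 reports "the number and percentage of subjects with a percentage reduction of 100%, ie, who are attack-free". The accompanying 95% intervals are Wilson intervals. SAP 10.2.1 states that the efficacy analyses "will be based on the overall Treatment/Efficacy evaluation period", which SAP Table 3 runs from the Day 1 Visit to the EOT Visit or the EOS date, whichever comes first.

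**Length of that period.** Protocol 3.4 plans at least 12 months of treatment and adds: "The treatment duration for each subject will be variable". It also allows the study to stop country by country. The Amendment 1 schedule has visits at Month 36 (Day 1081) and Month 42 (Day 1261), with Sponsor approval needed beyond Month 36.

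**Short follow-up.** SAP 10.2.1 says: "The secondary efficacy endpoints will be analyzed using the ATS Analysis Set". The same section allows exclusion for "insufficient time spent in the study which is defined as a Treatment/Efficacy evaluation period duration of less than 30 days", and SAP 10.5 extends this to every efficacy analysis: "All subjects who drop out without completing the first 30 days of the treatment period will be regarded as missing for all efficacy analysis". The protocol's efficacy section (10.3.2.1.2) names the same analysis set and states no minimum duration.

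**Time to event.** SAP 10.3.1 introduces the first-, second- and third-attack analyses with "The following events will be analyzed only for" treatment-naïve subjects. For all subjects it plans only maximum attack-free time: percentiles, range, and the shares reaching at least 6 and at least 12 months.

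**Windowed outputs.** SAP 10.2.2 plans attack-free percentages in successive 91-day windows, counting only subjects who complete the window, and a no-attack percentage for the first 31 days. Its cumulative windows from Day 1 cover the attack rate only.

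**The concern.** Staying attack-free gets harder the longer a subject is observed. One attack in 40 months removes a subject from the numerator, whereas a subject who leaves attack-free after a few months stays in it. The result is an average over whatever follow-up happened to occur, and its Wilson interval refers to no stated time point.

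This matters because SAP Table 5 repeats responder and attack-free rates by previous study and treatment, for Japanese subjects, for Chinese and Asian subjects, and for adolescents. The Japanese and Chinese groups are defined partly by site location, and closure can differ by country, so follow-up may differ between the groups being set side by side. SAP 4.5.1 also applies the same outputs at interim data cuts, so the percentage would be expected to drift down between cuts with no change in drug effect.

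The 30-day rule raises a separate issue. A treatment-naïve subject who has an attack on Day 5 and leaves on Day 20 has an observed first attack, and the rule discards it. Kaplan-Meier needs no minimum follow-up.

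**Working it through.** **Inputs.** The documents give no expected attack-free percentage and no early-dropout figure, so there is nothing of the plan's own to reproduce. The illustrative rate of 0.05 attacks per month is the phase 2 mean for 200 mg (protocol 1.2.3.2). The gamma shape k, the alternative rates, the follow-up mixes and the dropout counts are assumptions. N = 150 is the planned enrolment (protocol 3.5).

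**Step 1. Range of follow-up.** A Month 36 dose with EOT a month later gives Day 1111, or 1111/365.25 = 3.04 years. Day 1261 is 1261/365.25 = 3.45 years.

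**Step 2. Attack-free probability at t months.** With gamma-distributed subject rates, P(t) = [k/(k + rate × t)]^k.

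- Rate 0.05, k = 0.4, t = 12: (0.4/1.0)^0.4 = 69%.
- Rate 0.05, k = 0.4, t = 36: (0.4/2.2)^0.4 = 51%.
- Rate 0.15, k = 0.4: (0.4/2.2)^0.4 = 51% at 12 months and (0.4/5.8)^0.4 = 34% at 36.

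Other assumptions, with t = day/30.4375 (Poisson: P = exp(−rate × t)):

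| Rate per month | Model | Day 361 | Day 1081 |
|---|---|---|---|
| 0.05 | Poisson | 55.3% | 16.9% |
| 0.05 | k = 1 | 62.8% | 36.0% |
| 0.05 | k = 0.3 | 72.1% | 56.0% |
| 0.02 | k = 1 | 80.8% | 58.5% |
| 0.10 | k = 1 | 45.7% | 22.0% |

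The size of the fall depends on the assumptions; its direction does not.

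**Step 3. Same drug effect, different follow-up mixes** (rate 0.05, k = 1; true 12-month probability 62.8%). The crude figure is the weighted sum of P(t). For the third mix: 0.05 × 87.1 + 0.20 × 62.8 + 0.50 × 45.8 + 0.25 × 36.0 = 48.8%. The Kaplan-Meier column is the mean of 1,500 simulated trials of 150.

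| Assumed follow-up mix | Crude % | Kaplan-Meier at about 12 months |
|---|---|---|
| All 361 days | 62.8 | 62.8 |
| 10% 90 d, 60% 361 d, 30% 541 d | 62.3 | 62.8 |
| 5% 90 d, 20% 361 d, 50% 721 d, 25% 1081 d | 48.8 | 62.9 |
| 5% 90 d, 45% 1081 d, 50% 1261 d | 36.8 | 62.8 |

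**Step 4. Effect of the 30-day rule on the crude percentage.** Planned figure against the two extremes for those excluded:

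| Early dropouts of 150 | As planned | None attack-free | All attack-free |
|---|---|---|---|
| 3 | 88/147 = 59.9% | 88/150 = 58.7% | 91/150 = 60.7% |
| 8 | 85/142 = 59.9% | 85/150 = 56.7% | 93/150 = 62.0% |

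The shift is −1.2 to +0.8 points with 3 dropouts and −3.2 to +2.1 with 8.

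**Step 5. Do the other planned outputs close the gap?**

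- 91-day windows: fixed length, but each stands alone and drops non-completers. They do not give the chance of remaining attack-free from Day 1 to a later month.
- First 31 days: one month only.
- Cumulative windows: the right horizon, but for the attack rate.
- Maximum attack-free time of at least 6 or 12 months: covers all subjects, but longer observation gives more chance of reaching the threshold.
- Proportion of attack-free days (SAP 10.2.2.2): adjusted for duration, but a different quantity.

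**The case against.** The strongest reply is that the plan already has fixed-length attack-free outputs, and that restricting the first-attack analysis to treatment-naïve subjects is deliberate. Both statements are true. The Day 1–91 window largely supplies a Month 3 figure, and Table 5 shows the windowed results by treatment-naïve status. SAP 8.3.2 calls the treatment-naïve time-to-event analysis the main one, and the protocol's exploratory time-to-first-attack endpoint (2.3.2) concerns CSL312-naïve subjects. For roll-overs already on CSL312, Day 1 of this study is not the start of treatment. That argues against one pooled curve, but not against a separate curve for them.

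It is also fair that attack-free status is one summary within a secondary, descriptive endpoint. The leading efficacy measure is the median time-normalized attack rate, which adjusts for duration. The primary endpoint, TEAEs, is untouched.

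A reader might infer more than the documents support:

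- *That the crude percentage flatters the drug.* With planned treatment of at least 12 months, longer follow-up lowers it, so it will often sit below the 12-month value.
- *That early failures are removed in the drug's favour.* The rule depends on duration, not outcome. The documents give neither the number of early leavers nor their attack status, and Step 4 shows movement either way.
- *That those subjects disappear.* SAP 10.2.1 lists them with the reason, and dosed subjects remain in the safety analyses.
- *That follow-up of about one month drives the problem.* It should arise only through early dropout or an interim cut. The spread from 12 to about 42 months does most of the work.

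**Conclusion.** The point stands in a limited form. No planned output gives an attack-free percentage from Day 1 through Month 6, 12 or 24 for all subjects, and the whole-period percentage cannot be compared between groups or data cuts whose follow-up differs. At 0.05 attacks per month the difference between 12 and 36 months is 18 points with shape 0.4 (69% to 51%). Across the other dispersions tried at that rate it runs from 16 points (k = 0.3) to 38 (Poisson). These figures illustrate sensitivity; they do not predict the trial's result, since dispersion and follow-up mix are assumed.

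The 30-day rule is the smaller issue: roughly 1 to 3 points on the crude percentage for 3 to 8 assumed early dropouts. It has no statistical purpose in a time-to-event analysis, where it discards observed events.

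The Kaplan-Meier alternative assumes that leaving is unrelated to attack risk. Early withdrawal may not meet that assumption, so reasons for early exit should be read alongside the curves. The change is worth making but does not affect the study's primary conclusion.

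**What to change.** 1. In SAP 10.3.1, add Kaplan-Meier attack-free estimates from Day 1 with 95% CIs at fixed months (for example 6, 12 and 24) for all ATS subjects. Present treatment-naïve and non-treatment-naïve subjects separately. Censor at end of observation and include subjects with under 30 days.
2. In SAP 10.2.1 and 10.5, limit the 30-day rule to summaries of subject-level rates and the percentages derived from them.
3. In SAP 10.2.1.2, keep the crude attack-free percentage but report the follow-up distribution with it, overall and in each subgroup shown.
4. Optionally, count early leavers as non-responders in a sensitivity analysis. This is a worst-case choice and need not be the main result.

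The cost is revised SAP wording and a few extra outputs; no new data are needed and the Kaplan-Meier method is already specified. The fixed-month figure may come out higher or lower than the crude one.

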10.6 Treatment Compliance

Information about administered doses is taken from the subject diary. Details about any issues with the dosing device (incomplete dose, device malfunction, use error) are recorded on the Device Event page of the eCRF.

The calculation of compliance will be based on the number of injections taken as planned and the number of planned injections:

$$\text{Compliance}[\%] = 100 \times \frac{\text{Actual Number of Injections Taken as Planned}}{\text{Planned Number of Injections}}$$

The number of planned doses is calculated and rounded down to the next integer as:

$$\text{Planned Number of Injections} = \text{floor}\left(\frac{\text{Duration of the treatment period [days]}}{30}\right)$$

As this calculation considers that the last dose should be taken 30 days prior to the EOT Visit, for interim analysis the following rule will be used instead for subjects still ongoing at the time of the data-cut:

$$\text{Planned Number of Injections} = 1 + \text{floor}\left(\frac{\text{Duration of the treatment period [days]}}{30}\right)$$

An injection counts as “taken as planned” if a dose is recorded in the eDiary and the “Incomplete Dose” field is not checked on the corresponding Device Event page. If necessary, dose diary data will be matched to data from the Device Event page by date and subject number.

For calculating treatment compliance, the loading dose is counted as a single injection.

The following summary will be provided using the ATS Analysis Set:

- Number of SC injections received,
- Overall compliance (%),
- Number and percentage of subjects with overall compliance categorized by < 80%, 80%-100% and >100%,
- Number of injections with not the full volume administered,
- Number of use errors,
- Number of device malfunctions by category of malfunction,
- Number of other issues.

Compliance data will be listed together with exposure date, see Section 11.1.

11 Safety Analyses

All safety analyses will be based on the Safety Analysis Set as defined in [Section 6.3](#).

In general, all tables stated to be provided for subgroups are conditional on there being at least 5 subjects in that subgroup who are included in the Safety Analysis Set.

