- K: The eDiary will be collected and deactivated for all subjects. For subjects who terminate the study early, the eDiary should be deactivated and collected either on date of early termination or at the Follow-up Visit as applicable. If the Follow-up Visit is conducted remotely, the device should be returned to the site.
- L: Subjects may use the on-demand medication of their choice to treat HAE attacks experienced during the study if that medication has previously been shown to be effective.
- M: Subjects will be dispensed study medication for at home self-administration. Only first administration will be at site.
- N: Subjects will complete the Medication Dosing Diary on the eDiary at Day 1 site visit and then monthly at home through the End of Treatment Visit.

Schedule of Assessments: Treatment Period for All Subjects Under Amendment 1

Study Period		Treatment Period						End of Treatment ^A	Final Visit / Follow-up Telephone Call ^B (2 months after End of Treatment Visit)
Month		12	18	24	30	36	42		
Visit Day		361	541	721	901	1081	1261		
Visit Window (Day) ^C		±4d	±4d	±4d	±4d	±4d	±4d	±4d	-14d
Study center visit		X	X	X	X	X	X	X	
Written informed consent for Amendment 1 and switch to CSL312 200 mg AI ^D		1 st day under Amendment 1							
Physical examination ^E		X	X	X	X	X	X	X	
Vital signs including body weight		X	X	X	X	X	X	X	
SGART and IGART ^F		X		X		X			
TSQM II (subjects ≥ 18 yrs), AE-QoL (subjects ≥ 18 yrs) & WPAI:GH (subjects ≥ 16 yrs) ^G		1 st day under Amendment 1							
Urine collection for urinalysis (central lab) ^H		1 st day under Amendment 1							
Blood Draws (central lab)^I	Hematology / biochemistry / coagulation ^J	X		X		X		X	
	Retention sample for HAE biomarkers ^K	1 st day under Amendment 1							
	Pharmacokinetics / Pharmacodynamics	X	X	X	X	X		X	
	Immunogenicity	X		X		X		X	
Pregnancy test ^L		X	X	X	X	X	X	X	
Review eDiary / assess / document HAE attacks		X	X	X	X	X	X	X	X ^M
eDiary deactivation ^N								X	
Confirm plan for managing potential attack ^O		X	X	X	X	X	X		
IRT CSL312 kit assignment		X	X	X	X	X	X		
CSL312 accountability		X	X	X	X	X	X	X	
Administration of CSL312 ^P		X	X	X	X	X	X		
Concomitant medications and therapies		X	X	X	X	X	X	X	X
Adverse events		X	X	X	X	X	X	X	X

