4.3.3 Procedures for Handling Withdrawals

If a subject is withdrawn from the study, attempts will be made to complete and document the End of Treatment Visit assessments. If the subject is withdrawn from the study after receiving CSL312, every effort will be made to ensure that the relevant safety assessments are completed. The subject may also be asked by the investigator to complete other study assessments.

If the subject withdraws from the study and also withdraws consent for disclosure of future information, the Sponsor may retain and continue to use any data collected before such withdrawal of consent.

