6.4 Per Protocol Analysis Set

The Per-protocol (PP) Analysis Set comprises all subjects in the ATS Analysis Set who receive at least 1 dose of IP and who comply with the protocol. Decisions regarding exclusion from the PP Analysis Set will be made and documented before DBL.

Technical Note: unless stated otherwise below, the treatment will be considered the same whether administered with NSD or AI.

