8.4 Study Periods Relative to Treatment

AEs, HAE attacks, laboratory data, vital signs and other measurements will be assigned to the study time periods defined below.

Table 3 Definitions of Study Periods Relative to Treatment

Period	Start Date	End Date
Screening Period	Date of Informed Consent	Run-in Period Start Date
Run-in Period	Run-in Period Start Date	Day 1 Visit date of the Treatment Period or Date of Run-in Non-completion [whichever is first]
Treatment/Efficacy evaluation period	Date of Day 1 Visit of Treatment Period	Date of EOT Visit or EOS date [whichever is first]
Treatment/Efficacy before transition to AI evaluation period	Date of Day 1 Visit of Treatment Period	Date of first dose with AI – 1 Day (see Section 8.2.1)
Treatment/Efficacy after transition to AI evaluation period	Date of first dose with AI (see Section 8.2.1)	Date of EOT Visit or EOS date [whichever is first]
Follow-up	Date of EOT Visit	Date of Final/ Follow-up Visit
Safety evaluation period	Date and start time of First CSL312 Administration as entered in the eDiary	Date of Final/ Follow-up Visit
Safety Evaluation before transition to AI evaluation period	Date and start time of First CSL312 Administration as entered in the eDiary	Date of first dose with AI – 1 Day (see Section 8.2.1)
Safety Evaluation after transition to AI evaluation period	Date of first dose with AI (see Section 8.2.1)	Date of Final/ Follow-up Visit

The EOS date is the date entered in the Conclusion of Subject Participation eCRF page and should generally be identical to the date of the Follow-up Visit.

The handling of any unplanned dose changes or device changes will be discussed in the PARM. The safety evaluation period consists of the Treatment/Efficacy evaluation period plus the Follow-up Period.

Screening and Run-in periods will not be performed for roll-over subjects, instead relevant endpoint data (such as HAE attacks during the Run-in period) will be used from the CSL312_2001 and CSL312_3001 studies.

The duration of the Efficacy evaluation and the Safety evaluation period in days will be calculated as:

End Date – Start Date + 1 Day.

Screening, Run-in and Follow-up periods in days will be calculated as:

End Date – Start Date.

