9.2 Protocol Deviations

All identified protocol deviations throughout the study will be listed prior to DBL and will be classified into minor/major by CSL. Major protocol deviations are defined as deviations that could have a significant effect on the subject's safety, rights, or welfare and/or on the integrity of the study data.

The protocol deviations' classification into minor and major will be reassessed under statistical considerations. During the PARM, the classification and the subject's assignment to

the analysis sets will be discussed in detail. The Planned Analysis Review report will include these decisions and classifications and will be approved before each data-cut for interim analyses and prior to DBL for final analysis.

Possible major protocol deviations especially include the following but are not limited to:

Potential Major Protocol Deviations	Potential Exclusion From Analysis Set
Subject did not provide informed consent (informed consent date missing)	Screening, Safety, ATS, PP, PK, PD
Subject assigned to treatment but not treated with study treatment	Safety, PP, PK, PD
Subject assigned to treatment and treated but does not have at least one measurable PK concentration	PK
Subject assigned to treatment and treated but does not have at least one PD measurement	PD
Subject assigned to treatment and treated but violated inclusion or exclusion criteria	PP, potentially others to be discussed during the PARM
Subject assigned to treatment and treated but treatment compliance outside 80-120%	PP, potentially also PK, PD
Subject assigned to treatment and treated but received prohibited concomitant medication	PP, potentially also PK, PD

Presumably other protocol deviations will be classified as major and lead to the exclusion of subjects or data from analysis sets.

Prior to the PARM, a list of concomitant medications used in the study will be provided to CSL as an Excel file in the same format as the corresponding listing of concomitant medications in the table, figure, and listing (TFL) shells. This Excel file will be reviewed by CSL and concomitant medication potentially interfering with the PK/PD analysis or with the efficacy analysis will be flagged. Subjects with such a concomitant medication flagged may be excluded from the respective analysis set.

The following listings will be provided using the Screened Analysis Set:

- Planned and actual treatment.

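### SAP 10.6 counts one planned injection too few when the treatment period ends 28 days or less after the last dose, so on-schedule subjects can score above 100% and, after 2 to 5 doses, above the 120% limit in SAP 9.2

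*SAP*

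**What the plan says.** SAP 10.6 defines compliance as injections taken as planned divided by planned injections. Planned injections are the treatment-period duration in days divided by 30, rounded down. The SAP gives the premise: "As this calculation considers that the last dose should be taken 30 days prior to the EOT Visit". It therefore adds one to the count in a single case: "for interim analysis the following rule will be used instead for subjects still ongoing at the time of the data-cut". The loading dose counts as one injection.

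SAP 8.4 counts the duration inclusively (end date minus start date plus 1) and ends the period at "Date of EOT Visit or EOS date [whichever is first". The summary in SAP 10.6, on the All Treated Subjects (ATS) set, includes "Number and percentage of subjects with overall compliance categorized by < 80%, 80%-100% and >100" per cent. SAP 11.1 puts the planned count and the compliance figure in the subject listing.

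SAP 9.2 lists, as a potential major deviation, "Subject assigned to treatment and treated but treatment compliance outside 80-120" per cent, with potential exclusion from the per-protocol (PP) set and possibly from PK and PD. SAP 6.4 restricts PP to ATS subjects who "receive at least 1 dose of IP and who comply with the protocol".

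On withdrawal, Protocol 4.3.3 says "attempts will be made to complete and document the End of Treatment Visit assessments" and gives no timing. The Protocol synopsis and Protocol 3.1 place the EOT visit 1 month after the last dose, in a sentence that also covers subjects who terminate early.

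**The concern.** The rule works only while its premise holds. The authors saw that it fails for a subject caught between doses, because they corrected it for subjects ongoing at an interim cut. No matching correction exists for a subject whose period has ended between doses. Such endings can occur: Protocol 4.3.2 allows withdrawal at any time, and the EOS date closes the period if it comes before EOT.

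Two things are at stake. The compliance table and listing would show subjects who took exactly the doses due as having taken more than planned. Some of them would also be put forward as potential major deviations although their dosing followed the schedule.

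**Working it through.** **Inputs.** Doses fall on Days 1, 31, 61 and so on (visit days in the Protocol schedules of assessments). D is inclusive (SAP 8.4). The visit window is ±4 days (Protocol Table 4; the Amendment 1 schedule shows it for EOT), so an in-window EOT falls 26 to 34 days after the last dose.

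**Formula.** With n doses on schedule and a period ending g days after the last one, D = 30(n-1) + 1 + g. SAP planned count = floor(D/30) = (n-1) + floor((g+1)/30).

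**The plan's own case.** At g = 30, floor(31/30) = 1, so planned = n and compliance is 100%. The same holds for every g from 29 to 34.

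**When it fails.** For g from 0 to 28, floor((g+1)/30) = 0, so planned = n-1 and the score is n/(n-1).

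| Doses taken | Period ends on Days | Planned (SAP) | Compliance | Against 80-120% |
|---|---|---|---|---|
| 1 | 1-29 | 0 | undefined | – |
| 2 | 31-59 | 1 | 200% | outside |
| 3 | 61-89 | 2 | 150% | outside |
| 4 | 91-119 | 3 | 133.3% | outside |
| 5 | 121-149 | 4 | 125% | outside |
| 6 | 151-179 | 5 | 120% | at the limit |
| 7 | 181-209 | 6 | 116.7% | inside |

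**Same dosing, different status.** Three doses by Day 75, ongoing at an interim cut: 1 + floor(75/30) = 3, so 100%. Withdrawn that day: floor(75/30) = 2, so 150%.

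**A missed dose can be hidden.** A subject who leaves on Day 105 with 3 of the 4 doses due (Days 1, 31, 61, 91) scores 3/floor(105/30) = 3/3 = 100%, where the doses due give 75%.

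**Completers.** EOT 2 to 4 days early means g = 28, 27 or 26, which is 3 of the 9 in-window days. With 12 doses, D = 357 to 359, planned = 11 and the score is 12/11 = 109.1%. With 24 doses it is 24/23 = 104.3%, and with 36 it is 36/35 = 102.9%.

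**Calendar-month dosing (30.4375 days).** With 12 doses the last falls on Day 336. EOT at g = 26 gives D = 362 and floor(362/30) = 12, so 100%. At 24 doses D = 727 and planned = 24; at 36 doses D = 1092 and planned = 36. These completers are unaffected. Early leavers still are: planned reaches n only from g = 28 at 3 doses and g = 27 at 5 doses.

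**The case against.** The strongest reply is that the Protocol schedules early terminators for an EOT visit 1 month after the last dose. A subject who follows that has D = 30n + 1, planned = n and compliance of 100%. This stands. A reader might infer that every early leaver is mis-scored, or that Protocol 4.3.3 fixes EOT at the moment of withdrawal. The documents support neither: 4.3.3 gives no timing, and the synopsis and 3.1 do. The error is confined to subjects whose EOT or EOS date falls 28 days or less after a dose.

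For the same reason, simply adding one for everyone who stops early would be wrong. With EOT 30 days after the last dose, 1 + floor((D-1)/30) gives n + 1 planned: 50%, 66.7% and 75% after 1, 2 and 3 doses, where the current rule gives 100%.

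A second reply is that exclusion is only potential. SAP 9.2 has classifications reassessed and discussed at the Planned Analysis Review Meeting (PARM), and the SAP 11.1 listing shows planned counts and percentages by subject. This also stands, but the meeting decides on analysis sets and does not correct the reported percentages.

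A third reply is that SAP 10.2.1 and 10.5 already set aside treatment periods under 30 days. That covers efficacy analyses only. The compliance table uses ATS without a minimum duration, so the zero denominator remains.

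**Conclusion.** The rule is wrong as written for a defined group: subjects whose period ends 28 days or less after the last dose. The size is exact on the 30-day schedule: 200% to 125% after 2 to 5 doses, exactly 120% after 6, undefined after 1, and at most 109.1% for completers with 12 or more doses and an in-window early EOT. The completer figures depend on 30-day dosing and disappear with calendar-month dosing. The documents do not give the number of early leavers, so the number affected is unknown.

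It is tempting to conclude that PP will lose early leavers, perhaps poor responders, and that the efficacy results are biased. The documents do not support this. Exclusion is not automatic. PP serves the baseline tables (SAP 9.3) and a second analysis of one secondary endpoint (SAP 10.2.1), and ATS carries the main efficacy results. Nor are completers with 12 or more doses pushed past 120%. The impact is minor: the compliance table and listing, and potential PP (possibly PK or PD) flags. The primary safety analysis and the ATS efficacy results are unaffected.

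**What to change.** Replace the final-analysis denominator in SAP 10.6 with two rules.

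- Completers, and early stoppers whose EOT falls 26 to 34 days after the last dose: planned = floor((D+3)/30). This equals (n-1) + floor((g+4)/30), which is n for g from 26 to 34. Example: floor((357+3)/30) = 12.
- Other early stoppers, whose period ends between doses: planned = 1 + floor((D-1)/30). This is n for g from 0 to 29. Example: Day 75 gives 1 + floor(74/30) = 3, so 100%.

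On the 30-day schedule, every on-schedule subject with a period ending 0 to 34 days after the last dose then scores 100%; this covers 1 to 42 doses. The Day 105 example scores 3/4 = 75%.

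Two limits should be stated. For an early stopper whose period ends 35 days or more after the last dose, the second rule counts the next dose as missed; the SAP should say whether that is intended after a decision to stop treatment. Under calendar-month dosing the second rule can count one dose too many from 12 doses on (12 doses, exit 25 days later: D = 361, planned 13, 12/13 = 92.3%), which stays inside 80-120%.

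Splitting the top category at 120%, to match SAP 9.2, is an optional display change.

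The cost is two formulas in one section, using dose dates, period end dates and completion status that are already collected. On the 30-day schedule, scores for periods ending 29 to 34 days after the last dose do not change. Calendar-month completers with an in-window EOT also keep their scores: with 36 doses, D = 1097 gives floor(1097/30) = 36 and floor(1100/30) = 36.
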